16.4.2.2 Haemostatic effect

Description of the haemostatic effect of N9-GP when used for treatment of bleeding episodes will be summarised and listed according to the four point scale for haemostatic response (poor, moderate, good and excellent).

Protocol
 Trial ID: NN7999-3895
 UTN: U1111-1135-9557
 EudraCT No.: 2012-004867-38

~~CONFIDENTIAL~~

| | | |
|----------|------------------|---------------------|
| Date: | 05 November 2019 | Novo Nordisk |
| Version: | 8.0 | |
| Status: | Final | |
| Page: | 99 of 119 | |

A success rate will be calculated based on counting good or excellent as successes and poor and moderate as failures and based only on reported outcomes.

For the calculation of the success rate the numerator will include all treated bleeding episodes with a reported haemostatic response of good or excellent, while the denominator will include all treated bleeding episodes with a reported haemostatic response. A sensitivity analysis will also be conducted where the denominator also includes treated bleeding episodes with missing response (i.e. missing response is counted as a failure).

Haemostatic effect will be determined based on haemostatic response for bleeding episodes occurring both during pre-prophylaxis and prophylaxis period.

Haemostatic response will also be summarised by type of bleeding.

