 Trial ID: NN7999-3895
 UTN: U1111-1135-9557
 EudraCT No.: 2012-004867-38

~~CONFIDENTIAL~~

Date: 05 November 2019
 Version: 8.0
 Status: Final
 Page: 66 of 119

Novo Nordisk

Table 8-3 4-point scale

| Classification | N9-GP dosing | Description |
|----------------|---|--|
| Excellent | 
 One dose within 8 hours | Abrupt pain relief and/or clear improvement in objective signs of bleeding |
| Good | 
 One dose within 8 hours | Noticeable pain relief and/or improvement in signs of bleeding |
| Moderate | 
 More than one dose within 8 hours | Probable or slight beneficial effect after the first injection |
| Poor | 
 More than one dose within 8 hours | No improvement or worsening of symptoms |

Re-bleed

Classification of re-bleed will be performed at the time of the statistical analysis, according to the following criteria:

A re-bleed is defined as a new bleeding episode within 72 hours after stopping of a previous bleeding episode at the same or a subset of the same anatomical locations

If a bleeding episode occurs in the same location later than 72 hours after stopping the treatment it is considered as a new bleeding episode

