16.4.2.4 FIX consumption

Amount of N9-GP used for prophylaxis (IU/Kg/month/year) and amount consumed per bleeding episode (number of doses and IU/kg bw/bleeding episode) will be summarised and listed.

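### The haemostatic success rate ignores re-bleeds: a bleed rated good or excellent stays a success if it returns at the same site within 72 hours, so the rate may overstate lasting haemostasis

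*Protocol*

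**What the plan says.** Protocol section 16.4.2.2 dichotomises the four-point scale by "counting good or excellent as successes and poor and moderate as failures and based only on reported outcomes". In the rate itself, "the numerator will include all treated bleeding episodes with a reported haemostatic response of good or excellent". Every treated bleed that was rated goes into the denominator. The one sensitivity analysis planned there is for absent ratings: "missing response is counted as a failure".

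Table 8-3 in section 8.6.1 attaches the same dosing condition to excellent and good: "One dose within 8 hours". Moderate and poor need more than one dose in that window.

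The same section then says: "A re-bleed is defined as a new bleeding episode within 72 hours after stopping of a previous bleeding episode", at the same location or a subset of it. It adds: "Classification of re-bleed will be performed at the time of the statistical analysis". The sentence after the definition treats a same-site bleed as new once more than 72 hours have passed since treatment was stopped.

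On doses, section 16.4.2.4 says only that the "amount consumed per bleeding episode (number of doses and IU/kg bw/bleeding episode) will be summarised and listed".

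**The concern.** The protocol defines a re-bleed, gives it a time window and commits to classifying it at analysis. Nothing in section 16 then uses it. A family whose child bled, was treated, and bled again in the same joint two days later would hardly call the first treatment a full success, yet the planned rate does.

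Section 4.2.2 stars haemostatic effect as a key supportive secondary endpoint for public posting and also lists doses needed to treat a bleed. Section 16.6 says the main report will cover all endpoints and form the basis for the paediatric indication. Section 3.4 already cites single-dose control as a benefit seen in the pivotal trial (99% of bleeds in the 40 IU/kg arm). Readers will take a high success rate and a mean near one dose per bleed as evidence of lasting control, but the plan does not show whether the control lasted.

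**Working it through.** **Step 1. Does a re-bleed change the first rating?** The numerator in 16.4.2.2 has no re-bleed condition. The rating in Table 8-3 depends on dosing within 8 hours, and no rule revises it later. The only episode-merging rule in section 16 covers several locations bleeding from one event or at one time point. The SAP is confined to neurocognitive data (SAP section 6), so it adds nothing here.

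- If re-bleeds are separate episodes, the first bleed keeps its rating and the re-bleed enters with its own, possibly as a second success.
- If re-bleeds are merged, no rule turns the first rating into a failure.

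So a bleed rated good or excellent that returns after the 8-hour window stays a success on either reading.

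**Step 2. Is the re-bleed its own episode?** Section 8.6.1 supports both answers. Its definition calls the re-bleed a new episode within 72 hours. The next sentence reserves that status for a bleed after 72 hours, which implies an earlier one is not new. The clock also differs: end of the bleed in the first sentence, end of treatment in the second.

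**Step 3. Assumed worst case.** The documents give no success rate, target or re-bleed frequency, so there is no planned figure to reproduce and every input here is assumed. Take 100 recorded bleeds with 95 successes. Of those successes, r are re-bleeds whose first bleed was also a success. Each recorded bleed had one dose.

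- Separate counting: 95/100 = 95.0%.
- Merged, first rating kept: (95 − r)/(100 − r).
- Merged, counted as a failure: (95 − 2r)/(100 − r).
- Mean doses per bleed: 100/100 = 1.00 separate, 100/(100 − r) merged.

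| r | Separate | Merged, rating kept | Merged, failure | Doses per bleed, merged |
|---|---|---|---|---|
| 3 | 95.0% | 92/97 = 94.8% | 89/97 = 91.8% | 1.03 |
| 5 | 95.0% | 90/95 = 94.7% | 85/95 = 89.5% | 1.05 |
| 10 | 95.0% | 85/90 = 94.4% | 75/90 = 83.3% | 1.11 |

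The total drop is 3.2, 5.5 and 11.7 points. Double counting accounts for 0.2, 0.3 and 0.6 of it. The rest comes from calling the pair a failure.

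**Step 4. Less extreme assumptions.** Let p be the success proportion among first bleeds, f the number of re-bleeds per first bleed (unrelated to the first rating), and q the success proportion among re-bleeds. Separate counting gives (p + qf)/(1 + f). Merging as a failure gives p(1 − f). Merging with the rating kept gives p.

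With p = 0.90 and f = 0.05:

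- q = 0.90: (0.90 + 0.045)/1.05 = 90.0%, against 0.90 × 0.95 = 85.5% (4.5 points higher).
- q = 0.50: (0.90 + 0.025)/1.05 = 88.1%, against 85.5% (2.6 points higher), or against 90.0% with the rating kept (1.9 points lower).

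For p from 0.80 to 0.95 and f from 0 to 10%, separate counting exceeds the merged-as-failure rate by 0 to 9.5 points. With f = 0 there is no difference.

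**Step 5. A case in the other direction.** Take 100 recorded bleeds, 90 successes, and three pairs in which bleed and re-bleed are both rated poor. Separate counting gives 90/100 = 90.0%. Merging each pair as one failure gives 90/97 = 92.8%. Here separate counting is the stricter rule.

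**The case against.** The strongest reply is that the endpoint is the response on the four-point scale, that the scale is tied to 8 hours, and that the rate is correct for what it defines. Haemostasis to 72 hours is a different quantity. That stands: the planned rate is not an error and need not be replaced.

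A reader might go further and infer that the rate is overstated, or that the rule can only flatter the product. The documents do not support this. They give no re-bleed frequency, and Step 5 shows the direction can reverse. Nor do they state that a re-bleed is counted as a second success or that its doses are split; both follow only if re-bleeds are separate, which section 8.6.1 leaves open.

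Three further points have force:

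- The definition of a re-bleed sets no condition on cause. A fresh injury at the same site within 72 hours would be classified as a re-bleed, and scoring it as a treatment failure would be harsh. Section 8.6.1 records cause, so the two can be told apart.
- If re-bleeds are separate, those treated during prophylaxis raise the annualised bleeding rate (16.4.2.1), which counts against the product.
- There are no confirmatory secondary endpoints (16.4.1), and no test, margin or target depends on this rate. Responses and doses will be listed, so re-bleeds could be traced afterwards.

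These limit the weight of the point. They do not explain why a classification the protocol plans to make is used nowhere.

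**Conclusion.** The point holds as a gap in the plan. On either reading of section 8.6.1, a bleed rated good or excellent that returns at the same site after the 8-hour window but within 72 hours remains a success. The rate may therefore overstate lasting haemostasis.

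The size and direction of any effect depend on how many bleeds re-bleed and which ones, and the documents are silent on both. The figures of 91.8%, 89.5% and 83.3% against 95.0% are an assumed worst case in which every re-bleed is a success that follows a success. They should be quoted only with that label. The inconsistency over episode status and the 72-hour start is in the text and needs no assumption. Because the endpoint is supportive and descriptive, this is a low-priority improvement.

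**What to change.** Before the next database lock:

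1. Keep the planned success rate unchanged.
2. Reconcile the two sentences in section 8.6.1: state whether a re-bleed is merged with the first bleed or is its own episode, and whether the 72 hours run from the end of the bleed or the end of treatment.
3. Beside the rate, report the number of re-bleeds by cause (spontaneous or traumatic).
4. In 16.4.2.2, add a sensitivity analysis in which a bleed followed by a classified re-bleed is one episode counted as a failure, alongside the existing analysis for missing ratings.
5. In 16.4.2.4, also present doses and IU/kg summed over the bleed and its re-bleed.

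No new data are needed. Start and stop times, location, cause and each dose are already collected under section 8.6.1, and the classification is already planned. The cost is a clarified definition, one count, one sensitivity row and one extra dose summary. The downside for the sponsor is a possibly lower success rate in the sensitivity analysis and slightly higher doses per bleed.

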8.2.3 Treatment of bleeding episodes in low titre inhibitor patients < 5 BU

Bleeding episodes in low titre inhibitor patients that do not respond sufficiently to N9-GP treatment may in addition be treated with bypassing agents according to local label for a period of up to 2 years. It is recommended to avoid FIX containing bypassing agents. Patients will stay in the trial and continue the 40 IU/kg N9-GP treatment. The time of administration of other haemostatic medication (including bypassing agents) should be entered in the eCRF/eDiary.

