8.2.4 Prohibited medication

Treatments with other FIX concentrates are not allowed, during the course of the trial.

If possible, use of Tranexamic acid should be avoided.

Heparin sealing of central venous access ports and cannula is allowed.

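### The haemostatic success rate has no rule for bleeds in which a bypassing agent was added after N9-GP, so it may credit N9-GP with another drug's effect

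*Protocol*

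**What the plan says.** Protocol section 16.4.2.2 sets out to give a "Description of the haemostatic effect of N9-GP when used for treatment of bleeding episodes". Success is defined by "counting good or excellent as successes and poor and moderate as failures and based only on reported outcomes". For the numerator, "the numerator will include all treated bleeding episodes with a reported haemostatic response of good or excellent"; for the denominator, "the denominator will include all treated bleeding episodes with a reported haemostatic response". The only sensitivity analysis adds bleeds with a missing response to the denominator as failures.

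The ratings come from Table 8-3 in section 8.6.1. Each category has a dosing condition, headed as N9-GP dosing, and a description. Excellent and Good require a single dose within the 8-hour window; Moderate and Poor list more than one. The description of Excellent is "Abrupt pain relief and/or clear improvement in objective signs of bleeding".

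On other drugs, section 8.2.3 states: "Bleeding episodes in low titre inhibitor patients that do not respond sufficiently to N9-GP treatment may in addition be treated with bypassing agents". Section 5.3.6 says the same, for up to 2 years, with the patient staying in the trial on N9-GP. Section 8.2.3 adds: "The time of administration of other haemostatic medication (including bypassing agents) should be entered in the eCRF/eDiary". Section 8.2.4 does not allow other FIX concentrates, but on tranexamic acid says only: "If possible, use of Tranexamic acid should be avoided".

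The supplied SAP covers neurocognitive data only (SAP section 6) and is silent on this endpoint.

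**The concern.** Adding a bypassing agent under section 8.2.3 presupposes that N9-GP did not work sufficiently for that bleed. Section 16.4.2.2 ignores this and takes the reported rating as it stands. A bleed that N9-GP did not control, but that improved after the second agent, can therefore enter the numerator of a rate presented as the effect of N9-GP.

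Haemostatic effect is one of the secondary endpoints marked in section 4.2.2 for registry posting. The trial is single-arm (section 5.1), so no comparator would carry the same distortion. The affected bleeds would come from patients with low titre inhibitors, where the effect of N9-GP is most in question. The missing-response sensitivity analysis cannot reveal the problem, because these bleeds have a response.

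**Working it through.** **Step 1: follow one bleed through the rules.** Take a hypothetical low titre inhibitor patient given N9-GP at 0 h without adequate effect, a bypassing agent at 3 h, and showing clear improvement at 6 h.

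| Rule | Result for this bleed |
|---|---|
| Section 16: bleed treated with N9-GP | Met; the bleed enters the endpoint |
| Table 8-3 dosing, Excellent and Good: one N9-GP dose within 8 h | Met |
| Table 8-3 dosing, Moderate and Poor: more than one N9-GP dose within 8 h | Not met |
| Table 8-3 description, Excellent: clear improvement | Met at 6 h, after the bypassing agent |
| Table 8-3 descriptions, Moderate and Poor: slight effect after the first injection, or no improvement | Either could describe the state before 3 h |
| Section 16.4.2.2: condition on other drugs | None |

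No row fits cleanly. The dosing column points to success; the descriptions point to success or failure depending on when, and to which drug, the rater attributes the improvement. If the report says good or excellent, the bleed is a success.

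**Step 2: size of the effect.** The plan gives no expected success rate, bleed count or precision for this endpoint, so there is no figure of its own to reproduce. Let N be the number of rated bleeds, S the number rated good or excellent, f the share of rated bleeds given a bypassing agent between N9-GP and the rating, and g the share of those rated good or excellent.

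- As-rated rate: S/N
- Rate with these bleeds as failures: (S − f·g·N)/N
- Difference: f·g

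Neither f nor g is in the documents. Assuming S/N = 90/100:

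| f | g | Counted as failures | Difference, points |
|---|---|---|---|
| 0 | any | 90% | 0 |
| any | 0 | 90% | 0 |
| 1% | 50% | 89.5% | 0.5 |
| 2% | 100% | 88% | 2 |
| 5% | 50% | 87.5% | 2.5 |
| 5% | 100% | 85% | 5 |
| 10% | 100% | 80% | 10 |

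**Step 3: why a few patients can matter.** Assume, again without support in the documents, 40 patients followed for one year: 2 with low titre inhibitors and 38 others with 1 bleed each.

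- The 2 patients bleed 5 times each, and 25% of those bleeds are rescued and rated a success: 2 × 5 × 0.25 = 2.5 of 10 + 38 = 48 bleeds, or 5.2 points.
- They bleed 10 times each, and 50% are rescued and rated a success: 2 × 10 × 0.50 = 10 of 20 + 38 = 58 bleeds, or 17.2 points.

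These scenarios fix the share of such ratings above zero, so they show sensitivity and are not estimates.

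**Step 4: why exclusion is not a substitute.** Dropping these bleeds gives (S − f·g·N)/(N − f·N). With f = 5% and g = 50% this is 87.5/95 = 92.1%, above the as-rated 90%, because correctly rated failures leave the denominator too.

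**The case against.** The strongest reply is that the scale is meant to rate N9-GP itself. Section 16.4.2.2 names the N9-GP effect, Table 8-3 judges Moderate on what followed the first injection and makes Poor the category for no improvement, and section 6.4 equates a poor rating with treatment failure. A careful rater would call the example bleed moderate or poor. A reader might infer from the missing rule that the plan scores failed N9-GP treatment as success and that the rate is therefore overstated. The documents do not support that: no section says so, and it happens only if the rater credits N9-GP with the other drug's effect. This stands, and the conclusion is conditional for that reason.

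It does not close the gap. The Moderate and Poor dosing conditions do not match a single N9-GP dose, nothing tells the rater to disregard improvement after another drug, and during home treatment the parents enter the evaluation (section 8.8.3). The surgical scale in section 8.7.2 does treat a required change of regimen as part of Poor; the bleed scale has no counterpart.

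The following also stand:

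- Exposure is narrow. Bypassing agents are provided for only in low titre inhibitor patients, confirmed high titre patients stop N9-GP, and bleeds treated only with another agent fall outside the bleeding endpoints (section 16).
- A reader might infer that doses and IU/kg per bleed are also wrong. Section 16.4.2.4 reports N9-GP actually consumed, and one dose recorded as one dose is accurate.
- Failing every bleed given tranexamic acid, or another drug before N9-GP, would go too far for the main rate. Such use need not mean that N9-GP failed.
- The endpoint is descriptive and not confirmatory (section 16.4.1), and affected bleeds can be identified from recorded data. Section 16 allows a further SAP; whether one deals with this cannot be seen.

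**Conclusion.** The point holds in conditional form. Section 16.4.2.2 has no rule for bleeds given a bypassing agent after insufficient response to N9-GP, Table 8-3 lacks a failure category that fits one N9-GP dose followed by another agent, and the planned sensitivity analysis does not reach these bleeds. Where they are rated good or excellent, the success rate is overstated as a measure of N9-GP effect by exactly their share of all rated bleeds.

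That share is unknown. It is zero if no rated bleed is rescued or if all rescued bleeds are rated moderate or poor, and 0 to 10 points over the assumed range of f up to 10% and g up to 100%. Larger values need the concentrated bleeding assumed in step 3. The change is worth making because it affects a posted endpoint and is cheap, not because bias has been shown.

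**What to change.** In section 16.4.2.2:

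1. State that a bleed for which a bypassing agent was given after the first N9-GP dose and before the haemostatic rating counts as a failure in the success rate, whatever the rating.
2. Report the as-rated success rate as a sensitivity analysis.
3. List bleeds given tranexamic acid or any other haemostatic drug, and add a sensitivity analysis that counts these as failures.

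Optionally, in section 16.4.2.4, also show doses and IU/kg per bleed for bleeds treated with N9-GP alone.

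This changes the analysis only, not treatment. It needs a small merge of bleed records with the administration times already required by section 8.2.3. Section 8.6.1 lists the start and stop of the bleed and the time of each N9-GP dose, but no time for the rating; if that time is not held, the rule should name a substitute such as the recorded stop of the bleed. The cost is a success rate that may be slightly less favourable; the as-rated figure beside it shows by how much.

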16.4.2.3 FIX activity

Incremental recovery 30 minutes post dosing (IR_{30min}), FIX activity 30 minutes post dosing (C_{30min}), and trough FIX activity level will be assessed at visits according to [Table 2-1](#).

FIX trough level is defined as the activity recorded immediately before N9-GP injection is given and reported as IU/mL. IR_{30min} is defined as the rise in FIX activity per IU/kg administered and is recorded 30 minutes after the end of N9-GP injection, and reported as [IU/mL]/[IU/kg]. It is calculated as the pre-dose subtracted FIX activity recorded 30 minutes after ended N9-GP injection and dividing the administered dose (IU/kg body weight (bw)).

16.4.2.4 FIX consumption

Amount of N9-GP used for prophylaxis (IU/Kg/month/year) and amount consumed per bleeding episode (number of doses and IU/kg bw/bleeding episode) will be summarised and listed.

16.4.2.5 Safety endpoints

Adverse events including SAEs, MESI and development of HCP antibodies

Treatment emergent AEs (TEAEs, defined as AEs occurring after dosing with trial product) and treatment emergent SAEs (TESAEs) will be summarised by frequency of events and frequency of patients with any event. Similar summaries cross-classified by severity and by causal relation to trial product will also be made.

MESIs will be summarised similarly to AEs.

Furthermore, listings will be provided displaying all TEAEs and TESAEs including pertinent clinical information.

HCP antibodies will be listed.

Protocol
 Trial ID: NN7999-3895
 UTN: U1111-1135-9557
 EudraCT No.: 2012-004867-38

~~CONFIDENTIAL~~

| | | |
|----------|------------------|---------------------|
| Date: | 05 November 2019 | Novo Nordisk |
| Version: | 8.0 | |
| Status: | Final | |
| Page: | 100 of 119 | |

All additional safety parameters such as laboratory parameters, including calculation of estimated glomerular filtration rate (eGFR), and physical examinations, including neurological assessments, will be summarised and listed.

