Pegylation of proteins is a well-established technology which is used in the treatment of a variety of clinical disorders.² In repeat dose toxicity studies in animals, PEG was shown to be bio-distributed to blood in connective tissue and cytoplasm of epithelial cells of the choroid plexus of the brain, for further information refer to the current version of the Investigator's Brochure (IB)⁷. The potential clinical implications of these animal findings are unknown. No adverse neurological effects of PEG have been reported in infants, children, and adolescents exposed to N9-GP during clinical trials. The potential consequences of long term exposure have not been fully evaluated. Due to this theoretical safety concern regarding PEG, potential clinical effects of longer-term exposure to N9-GP with special emphasis on the choroid plexus and the two major excretion organs (liver and kidney) will be investigated in more detail (neurological examination, age-appropriate neurocognitive assessments and laboratory analyses of plasma PEG levels, liver and kidney parameters).

No safety issues have been identified in the completed and ongoing clinical trials with N9-GP and the risk/benefit ratio for N9-GP is therefore expected to be favorable. For further information refer to the current version of the IB⁷.

Protocol
Trial ID: NN7999-3895
UTN: U1111-1135-9557
EudraCT No.: 2012-004867-38

~~CONFIDENTIAL~~

| | | |
|----------|------------------|---------------------|
| Date: | 05 November 2019 | Novo Nordisk |
| Version: | 8.0 | |
| Status: | Final | |
| Page: | 23 of 119 | |

4 Objective(s) and endpoint(s)

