4.2.2 Secondary Endpoint

- Number and frequency of adverse events (AEs), serious AEs (SAEs) and Medical Events of Special Interest (MESI)*
- Number of breakthrough bleeding episodes during prophylaxis (annualised bleeding rate)*
- Haemostatic effect by 4-point haemostatic response scale (“excellent”, “good”, “moderate” and “poor”)*
- Incremental recovery at 30 minutes (IR30min), FIX activity at 30 minutes (C_{30min}) and trough level
- Amount of drug administered and number of doses needed to treat a bleeding episode

*Key supportive secondary endpoint prospectively selected for posting on (e.g. clinicaltrials.gov and EudraCT).

Protocol
 Trial ID: NN7999-3895
 UTN: U1111-1135-9557
 EudraCT No.: 2012-004867-38

~~CONFIDENTIAL~~

| | | |
|----------|------------------|---------------------|
| Date: | 05 November 2019 | Novo Nordisk |
| Version: | 8.0 | |
| Status: | Final | |
| Page: | 24 of 119 | |

5 Trial design

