Novo Nordisk A/S will be responsible for the statistical analysis.

The main statistical reporting of the trial will be performed when at least 20 patients have completed main phase (minimum 50 weeks) with at least 50 EDs and completed visit 23. Data from patients not yet having completed main phase and data from patients that have entered extension phase at this point will be included up to latest visit prior to this cut-off date. The data will be presented for the main phase and extension phase separately as well as combined. Except for the confidence interval for inhibitor rate and for annualised bleeding rate, the evaluation of data will be based on descriptive statistics, i.e. summary tables, listings and figures.

An updated statistical reporting of the trial with supportive data will be performed when at least 40 patients have had at least 100 EDs. Data from all patients will be included up to latest visit prior this cut-off date. The data will be presented for the main + extension phase and the extended prophylaxis period (beyond 100 EDs) separately as well as combined.

All data will be reported separately in a final report when the trial is completed.

[figure not shown]

Figure 16–1 Individual patient flow and time period for main trial report

Protocol
 Trial ID: NN7999-3895
 UTN: U1111-1135-9557
 EudraCT No.: 2012-004867-38

~~CONFIDENTIAL~~

| | | |
|----------|------------------|---------------------|
| Date: | 05 November 2019 | Novo Nordisk |
| Version: | 8.0 | |
| Status: | Final | |
| Page: | 97 of 119 | |

Multiple bleeding locations occurring from the same event (e.g. due to a fall) or at the same time point will be counted as one bleeding episode.

All bleeding endpoints will be evaluated based on bleeding episodes treated with N9-GP unless the bleeding was considered clinically insignificant (non-treatment requiring bleeding episode) and the associated treatment given was part of prophylaxis.

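### Adverse events are tabulated by period without an exposure-adjusted rate, although patient-time differs between the periods, so counts and percentages cannot be compared across them

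*Protocol*

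**What the plan says.** Protocol 16.4.2.5 states that treatment-emergent adverse events (TEAEs) and serious adverse events (TESAEs) "will be summarised by frequency of events and frequency of patients with any event", and that "MESIs will be summarised similarly to AEs". The word frequency is not defined and no time denominator is given. The key secondary endpoint in 4.2.2 is worded in the same terms.

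Section 16 fixes the periods. For the main report, "The data will be presented for the main phase and extension phase separately as well as combined". For the updated report, "The data will be presented for the main + extension phase and the extended prophylaxis period (beyond 100 EDs) separately as well as combined". For the final report it says only that "All data will be reported separately in a final report when the trial is completed", with no split. Apart from the intervals for the inhibitor rate and the annualised bleeding rate, "the evaluation of data will be based on descriptive statistics, i.e. summary tables, listings and figures".

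Bleeding is treated differently: 16.4.2.1 models bleeds during prophylaxis by negative binomial regression with an adjustment for exposure time, plus an over-dispersed Poisson sensitivity analysis. The SAP limits itself to neurocognitive assessments (SAP section 6) and adds nothing on adverse events.

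**The concern.** A count of events, or a percentage of patients with an event, grows with the time observed even when the risk per unit of time is constant. If two periods hold different amounts of patient-time, their counts and percentages differ for that reason alone, and a real change in risk can be masked or imitated.

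This matters here because adverse events, serious adverse events and medical events of special interest are a key secondary endpoint. Section 11.1 lists CNS and renal events among the latter, and section 3.4 says of PEG exposure that "The potential consequences of long term exposure have not been fully evaluated". A reader of the updated or final report will naturally look across the period columns to see whether risk changes with longer exposure. The protocol already adjusts bleeds for time, so the omission for adverse events is also inconsistent within the plan.

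A smaller issue compounds this. A TEAE is any event after dosing, with no stated end. Discontinuing treatment does not by itself end participation (6.4), and patients with a confirmed high-titre inhibitor have adverse events collected at three follow-up visits after N9-GP is stopped (8.1.11). Events off treatment therefore count as treatment-emergent, and the plan does not say what time should be set against them.

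**Working it through.** **Inputs from the protocol**
- First patient first visit 2 July 2014; planned last patient first visit 30 September 2020, stated as 75 months of recruitment; end of trial 30 October 2022 (section 7).
- Main phase: 50 exposure days, at least 50 weeks (section 16), longer with pre-prophylaxis (5.3.2).
- Extension: 50 further exposure days, about one year (8.1.6).

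**Plan's own figure.** 2 July 2014 to 30 September 2020 is 2,282 days; 2,282 / 30.44 = 74.97 months. The stated 75 months is reproduced.

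**Time per patient, weekly dosing from visit 1**
- Total follow-up: 3,042 days (8.3 years) for the first patient, 760 days (2.1 years) for the last.
- Main plus extension: 100 weeks = 700 days (1.92 years).
- Beyond 100 exposure days: 3,042 − 700 = 2,342 days (6.4 years) down to 760 − 700 = 60 days (0.16 years).

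**Assumptions not in the documents.** Constant event rate r, no withdrawals, entry uniform over the recruitment window unless stated. Expected counts are then proportional to patient-time, and the percentage of patients with any event is the mean of 1 − exp(−r × t).

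**Final cut-off: beyond 100 exposure days against main plus extension.** The final report's split is not stated, so the updated report's split is used. Mean follow-up is (3,042 + 760) / 2 = 1,901 days, and (1,901 − 700) / 700 = 1.72. Changing one assumption at a time:

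| Scenario | Count ratio |
|---|---|
| Uniform entry | 1.7 |
| Front-loaded entry, Beta(1,2) | 2.3 |
| Back-loaded entry, Beta(2,1) | 1.2 |
| Uniform, main phase 0.5 year longer | 1.2 |
| Uniform, main phase 1 year longer | 0.8 |

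Percentages of patients with an event, uniform entry:

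| r per year | Main + extension | Beyond 100 | Ratio |
|---|---|---|---|
| 0.1 | 17.4% | 26.8% | 1.5 |
| 0.3 | 43.7% | 57.0% | 1.3 |
| 1 | 85.3% | 86.4% | 1.0 |

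**Main report: extension against main phase.** Take N evenly spaced entries, cut-off when the 20th patient completes 50 weeks, and extension counted to 100 exposure days:

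| N | Cut-off (years) | Main patient-years | Extension patient-years | Ratio |
|---|---|---|---|---|
| 40 | 4.0 | 21.6 | 15.8 | 0.73 |
| 50 | 3.4 | 22.3 | 15.1 | 0.68 |
| 60 | 3.0 | 23.0 | 14.3 | 0.62 |

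**Updated report** (cut-off when the 40th patient reaches 100 weeks): beyond 100 against main plus extension is 1.63, 1.12 and 0.89 for N = 40, 50 and 60.

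**With rates.** Events divided by patient-years give a ratio of 1.0 between periods under constant risk, by construction.

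**The case against.** The strongest reply is that these tables are descriptive. Section 16 presents the periods side by side but plans no test and no claim of change over time. Section 16.6 bases the main conclusion on main-phase data and calls the later reports supportive. The PEG question has its own instruments in 3.4: neurological examination, neurocognitive assessment, plasma PEG, and liver and kidney parameters. Neurocognitive scores are plotted against years of exposure (16.5), and every TEAE is listed. All of this stands. It limits what could go wrong, but it does not make the period columns comparable.

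A reader might infer something stronger: that constant risk will appear as a several-fold rise with long-term exposure. The period beyond 100 exposure days does average 1,201 / 350 = 3.4 times the minimum main phase, and 2,342 / 350 = 6.7 times for the first patient enrolled. But section 16 does not list main phase alone against beyond 100 exposure days; more than six years is one patient's maximum, not the length of a period; and pre-prophylaxis lengthens the main phase and narrows the gap. For the split that is specified, the distortion is smaller and can reverse.

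Two further replies are partly right. Adverse-event collection stops at the end of the trial (11.2), so for patients who stay on treatment the open-ended TEAE definition changes little. And simple exact Poisson intervals would ignore repeated events within a patient, so the remedy has to allow for that.

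**Conclusion.** The concern holds in a limited form. Neither document specifies an exposure-adjusted adverse-event rate, patient-time is unequal between the displayed periods and between patients, and counts or percentages are therefore not comparable across periods. Even the combined column pools patients whose planned follow-up differs four-fold (3,042 / 760 days).

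The distortion is modest, not several-fold: about 1.7 on counts at the final cut-off, with a range of 0.8 to 2.3, and 1.0 to 1.5 on percentages for the rates shown. In the main report constant risk would look like a fall, to about 0.6 to 0.7. The sizes rest on assumed entry patterns, no withdrawals and assumed pre-prophylaxis lengths. The range comes from changing one assumption at a time, so it is not an outer limit. The spurious fall also depends on ending the extension at 100 exposure days, as 8.1.7 does; if all time after visit 23 were filed under extension, the ratio would be 0.87 to 1.41. Because size and direction both depend on these details, a reader cannot correct for them by eye.

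Reading the tables as plain counts and percentages is itself an inference from the undefined word frequency, though the natural one.

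**What to change.** Add to Protocol 16.4.2.5, or to an analysis plan covering safety, text such as:

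*TEAEs, TESAEs and each class of medical event of special interest will also be given as events per patient-year, by reporting period and overall, with 95% confidence intervals that allow for repeated events within a patient (negative binomial or over-dispersed Poisson, as in 16.4.2.1; exact Poisson where events are few). Events and time at risk will be counted over the same window, which starts at the first dose, includes pre-prophylaxis time, and ends at a stated point after the last dose. Any descriptive statement on change over time will rest on these rates.*

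The sponsor should state the length of that closing window, define what frequency means, and give the split for the final report. The existing counts and percentages can stay.

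The cost is a few table columns and one derivation. Exposure time for the bleeding rate covers prophylaxis only, so total exposure including pre-prophylaxis has to be derived separately. The rates remain descriptive: patients are older in later periods and some will have withdrawn, so a difference in rates between periods would not by itself show an effect of longer exposure.
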